10.4 Implant Visit

The Implant Visit must occur ≤150 days after the Baseline Visit. Females of child-bearing potential (not post-menopausal or surgically sterile) must be administered a urine pregnancy test within 2 weeks prior to the implant visit to confirm they are not pregnant.

Only investigators who are trained and experienced in implanting the SynchroMed II infusion system and trained by Medtronic on the study requirements will be qualified to perform the implant. The IDDS will be implanted per the investigator's standard procedures. Investigators performing the implant should obtain a final intra-operative fluoroscopy or anteroposterior and lateral x-ray to confirm catheter placement. Initial device interrogations and data uploads must be completed at implant and final interrogation prior to discharge.

The investigator may determine whether to initiate IT therapy at the Implant Visit or after the Implant Visit and up to the date of the Post-Op Visit. If IT therapy is initiated at the Implant, refer to Section 10.6 for IT Therapy Initiation requirements. PFMS dosing will be managed according to the IT PFMS administration and dosing parameters outlined in Section 10.13. If PFMS is not added to the pump at the Implant, then preservative-free sodium chloride can be used to fill the pump until the IT Therapy Initiation occurs.

Non-opioid medications and concomitant therapies may be utilized to manage post-operative pain for up to 14 days post implant. If IT Therapy is not being initiated at the Implant Visit, systemic opioids may be taken to manage post-operative pain but must be discontinued a minimum of 7 days prior to the date of IT Therapy Initiation. Medications prescribed for the treatment of pain will be collected during the study and documented in the subject's medical records and on the applicable Electronic Case Report Form(s) (eCRF).

Use of myPTM for each subject will be at the discretion of the investigator and subject.

Data Collection Requirements for the Implant Visit:

- Date systemic opioids were stopped, if prior to the implant
- Adjunctive pain management therapies utilized
- Confirm urine pregnancy test completed within 2 weeks prior to implant, if applicable
- Final AP and lateral fluoroscopic/x-ray images to confirm catheter tip location
- Device information, (including Model # and Serial/Lot #) will be collected for each of the following:
 - Pump
 - Catheter
 - myPTM (if distributed)
- Initial and final device interrogation reports (at implant and prior to discharge)
- Pain medications
- AEs/DDs

10.5 Post-Op Visit

The Post-Op Visit must occur 14 days ± 4 days from the Implant Visit. Investigators should evaluate the subject's implant wound to confirm it has healed appropriately and document any relevant observations in the medical records (source records). The following activities must also be completed during the visit: initial and final device interrogations and data uploads, if device was interrogated, date systemic opioids were stopped (if after implant), pain medications, AEs and DDs must be documented in the subject's source.

Use of myPTM for each subject will be at the discretion of the investigator and subject.

If IT therapy is initiated at this visit, refer to Section 10.6 for IT Therapy Initiation requirements. PFMS dosing will be managed according to the IT PFMS administration and dosing parameters outlined in Section 10.13.

Data Collection Requirements for the Post-Op Visit:

- Date systemic opioids were stopped, if after implant
- Initial and final device interrogation reports
- Pain medications
- AEs/DDs

10.6 IT Therapy Initiation

IT Therapy Initiation may take place any time from the Implant Visit through the Post Op Visit. Subjects will be asked to complete the VAS for pain intensity and the NOSE assessment tool prior to site personnel performing other visit activities. If the IT Therapy Initiation is occurring on a date other than during the Implant Visit, or the Post-Op Visit, females of child-bearing potential (not post-menopausal or

surgically sterile) must be administered a urine pregnancy test at this visit to confirm they are not pregnant, before initiating IT PFMS. In addition, site personnel must confirm the drug testing results are negative for systemic opioids, cannabinoids, and illicit drugs.

Only PFMS and 0.9% solution of preservative-free sodium chloride injection (USP) for dilution will be allowed in the pump from the IT Therapy Initiation Visit through the 6-Month Visit. PFMS dosing will be managed according to the IT PFMS administration and dosing parameters outlined in Section 10.13.

Use of myPTM for each subject will be at the discretion of the investigator and subject. If myPTM will be utilized, the physician may activate myPTM, program the pump accordingly, distribute myPTM to the subject and educate the subject on the use of the myPTM during this visit.

Data Collection Requirements for IT Therapy Initiation:

- VAS
- NOSE
- Date systemic opioids were stopped, if applicable
- Adjunctive pain management therapies utilized
- Urine pregnancy test, if applicable
- Drug testing results for systemic opioids, cannabinoids, and illicit drugs
- Drug information including:
 - Drug name
 - Lot #/identifier
 - Dose
 - Concentration
- Initial and final device interrogation reports
- Pain medications
- AEs/DDs

10.7 1-, 3-, and 6-Month Visits

Visits will be required at 1, 3, and 6 months after IT Therapy Initiation (**Day 0**). Visit windows are as follow for these visits:

1-Month Visit	30 days \pm 5 days after Day 0
3-Month Visit	90 days \pm 10 days after Day 0
6-Month Visit	180 days \pm 10 days after Day 0

Subjects will be asked to complete the VAS for pain intensity and the NOSE assessment tool prior to site personnel performing other visit activities. VAS and NOSE will be collected at all visits. PFMS dose adjustments may be made during these required follow-up visits or during unscheduled visits if

necessary, to manage subject pain or opioid-related side effects. PFMS dosing will be managed according to the IT PFMS administration and dosing parameters outlined in Section 10.13.

In the event the subject is unable to be managed on morphine monotherapy from the IT Therapy Initiation through the 6-Month Visit, a study deviation eCRF must be completed.

Data Collection Requirements for the 1-, 3-, and 6-Month Visits:

- VAS
- NOSE
- Urine pregnancy test, if applicable
- Drug testing results for systemic opioids, cannabinoids, and illicit drugs
- Actual residual and fill volume (if pump refill occurs during visit)
- Drug information (if pump refill occurs during visit) including:
 - Drug name
 - Lot #/identifier
 - Dose
 - Concentration
- Initial and final device interrogation reports
- Pain medications
- AEs/DDs

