10.3 Intrathecal Trial Visit

Site personnel must ensure the subject meets eligibility criteria prior to initiating any IT drug trial procedures. Subjects will be asked to complete the VAS for pain intensity and the NOSE assessment tool. The investigator must then confirm the subject's systemic opioid dose is \leq 60 MME prior to moving forward with the IT drug trial. Females of child-bearing potential (not post-menopausal or surgically sterile) must be administered a urine pregnancy test at this visit to confirm they are not pregnant. In addition, site personnel must confirm each subject's drug testing results for systemic opioids and confirm results are negative for cannabinoids and illicit drugs. If it is determined the subject no longer meets eligibility criteria, or they choose to withdraw early, the subject will be exited from the study according to Section 10.10.

The IT trial will be conducted according to the investigator's standard of care procedures. A successful IT trial will be determined by the investigator and documented accordingly.

If the investigator determines the IT trial was not successful, the subject will be considered a screen failure and will be exited from the study according to Section 10.10.

Data Collection Requirements for the IT Trial Visit:

- Inclusion/exclusion criteria
- VAS
- NOSE
- Adjunctive pain management therapies utilized
- Urine pregnancy test results, if applicable
- Drug testing results for systemic opioids, cannabinoids, and illicit drugs
- Date systemic opioids were stopped, if prior to trial
- IT trial method, drug name, lot number/identifier, dose(s) and concentration(s)
- Pain medications
- AEs

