10.13 IT PFMS Administration and Dosing

Intrathecal study drug will be administered using commercially available Medtronic SynchroMed II infusion systems. IT PFMS initiation and subsequent dosing adjustments are determined based on specific patient needs and clinician standard practices but must be within the following evidence-based consensus guidelines and remain in line with study dosing goals.

IT PFMS Dosing Goal:

To maintain or improve pain control and/or opioid-related side effects (compared to Baseline) with utilization of the lowest reasonable daily dose of IT PFMS following discontinuation of all systemic opioids and implant of the SynchroMed II infusion system.

PFMS, at a concentration not exceeding 25 mg/mL and 0.9% solution of preservative-free sodium chloride injection (USP) for dilution, will be the only drug allowed in the pump from the IT Therapy Initiation Visit through the duration of the study, if possible.

IT PFMS Dose Initiation Parameters:

IT PFMS may be initiated at Implant, the Post-Op Visit, or any time in between per investigator standard practice and patient-specific therapy needs. Standard guidelines for intrathecal PFMS dosing initiation include:

- A starting PFMS dose of 0.1 to 0.5 mg/day, or half the effective trial dose, with lower initial PFMS doses considered, as needed, dependent upon the duration of opioid holiday. Determination of IT PFMS dosing based on previous systemic opioid dosing is not recommended.
- A starting concentration to achieve an estimated pump refill interval of 120 days, but not to exceed 180 days

- Patients may initiate myPTM use at any point during the study.

IT PFMS Dose Adjustment Parameters:

Study investigators or appropriately trained and delegated designees experienced with the use, filling, and dose modification of the SynchroMed II infusion system will be responsible for administering and adjusting PFMS doses in this study. The investigator is responsible for overseeing and managing dosing in accordance with the IT dosing goal and the following instructions:

- IT PFMS dose increases or decreases can be made any time throughout the duration of study.

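### Protocol 10.6 exempts a start of intrathecal morphine at the Post-Op Visit from pregnancy testing, although Table 3 ticks the test; on the 10.6 text the last required test is 10 to 32 days old

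*Protocol*

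**What the plan says.** Continuous intrathecal morphine (PFMS) may begin on any date from implant to the Post-Op Visit. Protocol 10.13 states: "IT PFMS may be initiated at Implant, the Post-Op Visit, or any time in between per investigator standard practice".

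The pregnancy-test provisions around that start are these:

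- **Protocol 10.3, Intrathecal Trial Visit.** Women of child-bearing potential "must be administered a urine pregnancy test at this visit to confirm they are not pregnant". There is no exemption.
- **Protocol 10.4, Implant Visit.** They "must be administered a urine pregnancy test within 2 weeks prior to the implant visit to confirm they are not pregnant".
- **Protocol 10.5, Post-Op Visit.** "The Post-Op Visit must occur 14 days ± 4 days from the Implant Visit". No pregnancy test appears in the text or in the data list. For a start on that day: "If IT therapy is initiated at this visit, refer to Section 10.6 for IT Therapy Initiation requirements".
- **Protocol 10.6, IT Therapy Initiation.** The condition reads "If the IT Therapy Initiation is occurring on a date other than during the Implant Visit, or the Post-Op Visit, females of child-bearing potential", and the stated purpose of the test is "to confirm they are not pregnant, before initiating IT PFMS". The data list in the same section includes the test only where applicable.
- **Protocol Table 3 (section 10.11) and SAP Table 5-1 (section 5.2.3).** Both tick the test at IT Therapy Initiation with no footnote. Both leave the Post-Op cell blank. Both footnote the Implant tick to the two-week rule.

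**The concern.** The two exempted visits are not alike. An Implant start relies on a test that 10.4 has just required. A Post-Op start has nothing comparable: 10.5 hands the question to 10.6, and 10.6 waives it. A woman who starts a few days after surgery, between the visits, is therefore tested that day, while one who starts later, at Post-Op, need not be. The documents give no reason for checking the later start less closely, and the drug-test requirement in the same paragraph of 10.6 has no such exemption.

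The prose also conflicts with the schedule. A site working from Table 3 would test at a Post-Op start; a site working from 10.6 would not. Because 10.20 lists failure to collect required assessments as a deviation, the same omission is compliant under one part of the protocol and a deviation under another.

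What is at stake is a safety check. Pregnant women may not take part (inclusion criterion 10; section 11.2), and 10.6 itself says why the test comes before the drug. The gap concerns the start of continuous infusion. It does not concern first intrathecal exposure, which is normally at the IT Trial and has its own test.

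**Working it through.** The documents state no age for the last test, so there is no figure to reproduce. The ages follow from the visit windows.

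**Inputs**

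- Last required test before implant: 0 to 14 days before implant (10.4, reading two weeks as 14 days).
- Post-Op Visit: 14 ± 4 days, that is day 10 to 18 after implant (10.5, Table 2).
- 1-Month Visit: 30 ± 5 days, that is 25 to 35 days after the start (Table 2).
- 3-Month and 6-Month Visits: 80 to 100 and 170 to 190 days after the start (Table 2).

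**Age of the last required test when infusion starts, following the 10.6 text**

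Age = days from test to implant + days from implant to start.

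| Start | Calculation | Age (days) |
|---|---|---|
| Implant Visit | (0 to 14) + 0 | 0 to 14 |
| Between the visits | tested that day | 0 |
| Post-Op Visit, full window | (0 to 14) + (10 to 18) | 10 to 32 |
| Post-Op Visit, nominal day 14 | (0 to 14) + 14 | 14 to 28 |

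**Interval to the next required test, at 1 Month**

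- Post-Op start without a test: (10 to 32) + (25 to 35) = 35 to 67 days; on nominal days, (14 to 28) + 30 = 44 to 58.
- With a test at the start: 25 to 35 days; nominal 30.

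The plan accepts longer gaps later: up to 100 − 25 = 75 days between the 1- and 3-Month tests, and up to 190 − 80 = 110 days between the 3- and 6-Month tests. The interval alone is therefore not the problem; the missing check before infusion begins is.

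**A Post-Op start is a realistic case.** Systemic opioids may be taken for post-operative pain if intrathecal therapy is not started at implant, but they "must be discontinued a minimum of 7 days prior to the date of IT Therapy Initiation" (10.4). A woman who takes a dose on the day of implant cannot start before day 0 + 7 = 7. That leaves day 7 up to the Post-Op Visit on day 10 to 18.

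**The case against.** The strongest reply is that, read as a whole, the plan already contains the test. Table 3 ticks it at IT Therapy Initiation, the 10.6 data list names it, and section 10.1 says that Table 3 summarises the visit procedures. On that view a single clause is out of step, and the 10 to 32 days arises only if a site follows that clause. The condition stands: the range describes the 10.6 text, not what every site will do. It does not remove the problem. Section 10.1 places the detail in the visit sections, so following the prose is reasonable, and the data list's qualifier leaves open exactly what the exemption decides.

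The comma in the 10.6 condition also permits a reading under which Post-Op starts are tested. That reading is strained, and if it is what was meant, the wording needs the same correction.

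The practical argument has more weight. All 93 subjects were enrolled when version 3.0 was written. Within the windows, therapy starts no later than day 150 + 18 = 168 after Baseline, so a correction can help only women who have not yet started. Tests at Baseline, at the IT Trial and before implant, required contraception, and the duty to report a suspected pregnancy at once (11.2) already limit the risk. All of this stands, and it is why the point is minor.

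**Conclusion.** The concern holds. Section 10.6 waives the pregnancy test for one expressly permitted start, 10.5 does not supply it, and both schedule tables contradict the waiver. Under the 10.6 text, the last required test at a Post-Op start is 10 to 32 days old (14 to 28 on nominal day 14), against 0 days for a start between the visits and 0 to 14 days for a start at implant.

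This rests on the natural reading of the exemption, on visits within their windows, and on two weeks meaning 0 to 14 days. The number of women of child-bearing potential still awaiting initiation is not given and may be zero. No endpoint, estimate or analysis changes. Severity is minor.

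**What to change.** First establish whether any woman of child-bearing potential has yet to start therapy; if none has, nothing remains to correct prospectively. Otherwise:

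1. In Protocol 10.6, strike the Post-Op Visit from the exemption, so that only an Implant start is excused.
2. In Protocol 10.5, add to the data list a urine pregnancy test when intrathecal therapy is initiated at that visit.
3. In Table 3, footnote the IT Therapy Initiation tick: a start at the Implant Visit is covered by the test in the two weeks before implant. The same footnote in SAP Table 5-1 is optional.

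With this change, the test at a Post-Op start is done that day. The cost is one urine test per affected woman, which the schedule already shows, and a short wording change. Section 16.7 requires sponsor approval and IRB approval before implementation, so the change is best bundled with the next amendment. The documents mention no further amendment, and delay reduces the number of women who could benefit.

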10.8 Unscheduled Visits

Unscheduled visits may occur during the study for reasons including dose adjustments, programming adjustments, pump refills, medication changes (if subject is unable to be successfully managed on morphine monotherapy), AEs, and DDs.

Subjects will be asked to complete the VAS for pain intensity and the NOSE assessment tool prior to site personnel performing other visit activities.

PFMS dose adjustments may be made during unscheduled visits if necessary, to manage subject pain or opioid-related side effects. PFMS dosing will be managed according to the IT PFMS administration and dosing parameters outlined in Section 10.13 and pump refills will be handled as required in Section 10.12.

Data Collection Requirements for Unscheduled Visits:

- VAS
- NOSE
- Reason for the unscheduled visit
- Actual residual and fill volume (if pump refill occurs during visit)
- Drug information (if pump refill occurs during visit) including:
 - Drug name
 - Lot #/identifier
 - Dose
 - Concentration
- Initial and final device interrogation reports
- Pain medications
- AEs/DDs

10.9 System Modifications

A system modification must be reported in the event the catheter and/or pump require surgical modification. Programming of a new PFMS dose or refilling the pump are not considered system modifications. In the event of a system modification, the follow-up schedule for the subject will remain unchanged.

Data Collection Requirements for System Modifications:

- VAS
- NOSE
- Reason for system modification and all affected components
- Initial and final device interrogation reports for the existing pump
- Actual residual volume of existing pump
- Drug information (if pump refill occurs during visit) including:
 - Drug name
 - Lot #/identifier
 - Dose
 - Concentration
- Initial and final device interrogation reports for new pump, if applicable
- Pain medications
- AEs/DDs

10.10 Study Exit

Normal study completion occurs when the subject has completed the required study visits through the 6-Month Visit (refer to required procedures described in Section 10.7), at which time the subject will end their participation in the study and site personnel will then complete required eCRFs. If a subject has already completed their 6-Month visit, they will be brought into re-consent, and be exited from the

study. If the subject is an early withdrawal, refer to Section 10.21 for subject withdrawal or discontinuation procedures.

10.11 Schedule of Events

Table 3: Schedule of Events

Study Procedures, Tasks, and Data Collection (row) by Visit (column)	Baseline Visit (Enrollment)	Intrathecal Trial Visit	Implant Visit	Post-Op Visit	IT Therapy Initiation	1-Month Visit	3-Month Visit	6-Month Visit (Study Exit)	Unscheduled Visits
Informed Consent Process	✓								
Demographics	✓								
Inclusion/Exclusion Criteria	✓	✓							
Urine Pregnancy Test	✓	✓	✓ ¹		✓	✓	✓	✓	
Drug Test	✓	✓			✓	✓	✓	✓	
Adjunctive pain management therapies	✓	✓	✓		✓				
Back and Leg Pain/Surgical History	✓								
VAS	✓	✓			✓	✓	✓	✓	✓
NOSE Assessment	✓	✓			✓	✓	✓	✓	✓
IT PFMS Dose					✓	✓	✓	✓	✓
Fluoroscopy/x-ray			✓						
Device information (model, serial/lot #)			✓						
Drug information (name, lot #/identifier, dose & concentration)		✓			✓	✓	✓	✓	✓
Initial and final device interrogation reports			✓	✓	✓	✓	✓	✓	✓
Collect AEs/DDs	✓ ²	✓	✓ ²	✓	✓	✓	✓	✓	✓
Pain Medications	✓	✓	✓	✓	✓	✓	✓	✓	✓

¹Confirm pregnancy test completed within 2 weeks prior to implant visit

²Device Deficiencies will be collected and reported from the Implant Visit through the 6-Month Visit/Study Exit

10.12 Pump Refills

Pump refills will be performed by study investigators or appropriately delegated personnel experienced with the use, filling, and dose modification of SynchroMed II infusion system.

- Pump refill procedures may occur at scheduled or unscheduled visits.
- Careful monitoring of the refill schedule must be done to prevent reservoir depletion and potential adverse events.
- Any drug remaining in the pump reservoir at the time of refill should be removed and discarded, and the pump reservoir should be refilled (document the actual residual volume, the refill volume, the drug concentration, and dose in the subject's medical record).

Refer to Section 10.13, for managing IT PFMS dose increases and decreases, including information on dosing limits. Refer to the SynchroMed II Programmable Pumps Implant Manual for the complete instructions pertaining to pump refill procedures.

10.13 IT PFMS Administration and Dosing

Intrathecal study drug will be administered using commercially available Medtronic SynchroMed II infusion systems. IT PFMS initiation and subsequent dosing adjustments are determined based on specific patient needs and clinician standard practices but must be within the following evidence-based consensus guidelines and remain in line with study dosing goals.

IT PFMS Dosing Goal:

To maintain or improve pain control and/or opioid-related side effects (compared to Baseline) with utilization of the lowest reasonable daily dose of IT PFMS following discontinuation of all systemic opioids and implant of the SynchroMed II infusion system.

PFMS, at a concentration not exceeding 25 mg/mL and 0.9% solution of preservative-free sodium chloride injection (USP) for dilution, will be the only drug allowed in the pump from the IT Therapy Initiation Visit through the duration of the study, if possible.

IT PFMS Dose Initiation Parameters:

IT PFMS may be initiated at Implant, the Post-Op Visit, or any time in between per investigator standard practice and patient-specific therapy needs. Standard guidelines for intrathecal PFMS dosing initiation include:

- A starting PFMS dose of 0.1 to 0.5 mg/day, or half the effective trial dose, with lower initial PFMS doses considered, as needed, dependent upon the duration of opioid holiday. Determination of IT PFMS dosing based on previous systemic opioid dosing is not recommended.
- A starting concentration to achieve an estimated pump refill interval of 120 days, but not to exceed 180 days

- Patients may initiate myPTM use at any point during the study.

IT PFMS Dose Adjustment Parameters:

Study investigators or appropriately trained and delegated designees experienced with the use, filling, and dose modification of the SynchroMed II infusion system will be responsible for administering and adjusting PFMS doses in this study. The investigator is responsible for overseeing and managing dosing in accordance with the IT dosing goal and the following instructions:

- IT PFMS dose increases or decreases can be made any time throughout the duration of study.
- IT PFMS Dose adjustments (increase or decrease) completed outside of a protocol-required visit will be considered an Unscheduled Visit. Initial PFMS dose increases following implant may be higher depending on the starting IT PFMS dose. Subsequent increases should only be made in response to inadequate pain control with increases as low as possible, but not exceeding 25%, to achieve adequate pain control

